10.7 REPORTING OF SERIOUS ADVERSE EVENTS

All SAEs, irrespective of the circumstances or suspected cause, must be reported on a Serious Adverse Event Form by the Investigator to the Sponsor or designee within 24 hours of their knowledge of the event, preferably by email. Other means of transmission can be decided when email is not possible (fax).

The Sponsor and Medical Monitor will be notified of SAEs within 24 hours.

Contact details for reporting SAEs:

[REDACTED]

Contact details for Pharm-Olam Medical Monitor:

[REDACTED]

The SAE form should include a clearly written narrative describing signs, symptoms, and treatment of the event, diagnostic procedures, as well as any relevant laboratory data and any sequelae, in order to allow a complete medical assessment of the case and independent determination of the possible causality.

Follow-up and outcomes should be reported for all subjects that experience an SAE.

It is critical that the information provided on the Serious Adverse Event Form matches the information recorded in the EDC system for the same event. In addition, the same information is to be recorded in the source documents.

Copies of additional reports and documents should be sent when requested and applicable. Follow-up reports relative to the subject’s subsequent course must be submitted to CRO until the event has subsided or, in case of permanent impairment, until the condition stabilizes.

10.8 PREGNANCY

Subjects should not become pregnant during the study.

The Investigator must report any pregnancy which occurs in a female subject or the female partner of a male subject up to 60 days after dosing by faxing the pregnancy form to the Sponsor or designee within 24 hours of the study site staff becoming aware of the pregnancy. The Investigator or study site staff must report the outcome of the pregnancy to the Sponsor or designee.

Contact details:

[REDACTED]

Pregnancy is not an SAE, however congenital abnormalities and birth defects in the offspring of male or female subjects should be reported as an SAE if the subject was pregnant during the study treatment period or in the 60-day period after dosing of study drug.

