7.1 TIMING OF ASSESSMENTS

If the following assessments are planned at the same time, the order of assessments should be as follows:

- 1) Influenza Patient Reported Outcomes questionnaire
- 2) Vital signs
- 3) Nasopharyngeal swab
- 4) Blood sampling

7.1.1 *Screening Examination and Eligibility Screening Form*

All subjects must provide written informed consent before any study specific assessments or procedures are performed.

Subjects will be assigned a unique screening number prior to Rapid Antigen Testing. Following confirmation of influenza A infection, subjects will be assessed for inclusion and exclusion criteria and those who fulfill all the inclusion and none of the exclusion criteria will be randomized into the study.

A screen failure log must be maintained by the Investigator for all entry criteria failures.

7.1.2 *Contraception Requirements*

All women of childbearing potential and all male subjects must practice effective contraception from screening until 60 days post-infusion. For the purposes of this study, women who do not meet one of the following criteria listed below are considered to be physiologically capable of becoming pregnant and are, therefore, defined as women of childbearing potential:

- Non-childbearing potential:
 - Post-menopausal: ≥ 12 months of natural (spontaneous) amenorrhea or
 - 6 weeks after surgical bilateral oophorectomy with or without hysterectomy or
 - follicle stimulating hormone > 40 mIU/mL
 - hysterectomy
 - bilateral tubal ligation

Women of childbearing potential and all male subjects participating in heterosexual sexual relations must be willing to practice effective contraception from screening until 60 days post-infusion. For the purposes of the study, highly effective contraception is defined as:

- Combination of an established form of hormonal contraception (oral, injected, or implanted) or an intrauterine device or intrauterine system

and

- A physical barrier method of contraception with use of a spermicide such as condom or occlusive cap (diaphragm or cervical/vault caps) with spermicidal foam/gel/film/cream suppository. The use of barrier contraceptives should always be supplemented with the use of a spermicide, unless not available in a country
- Male vasectomy with negative semen analysis documentation. The use of contraception does not apply if the male partner has been vasectomized at least 6 months prior to dosing

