- Complete abstinence can be considered an acceptable method of contraception at the discretion of the Investigator. Periodic abstinence (e.g., calendar, ovulation, symptothermal, or post-ovulation methods) and withdrawal are not considered acceptable methods of contraception

The combination of 2 barrier methods, periodic abstinence (e.g., calendar, ovulation, symptothermal, or post-ovulation methods), and withdrawal are not considered acceptable methods of contraception.

Pregnancy reporting is described in Section 10.8.

7.1.3 *Procedures for Enrollment of Eligible Subjects*

Once a subject has fulfilled the entry criteria, he/she will be assigned a unique identifier. The site will randomize the subject using the Interactive Web Response System (IWRS).

7.1.4 *Clinical Assessments and Procedures*

When required, subjects may be given a pre-screening informed consent in order to perform the Rapid Antigen Test for influenza. Flu-positive subjects will then be given a full explanation of the nature of the study and written informed consent (approved by the local ethics committee) will be obtained according to local requirements before any study-related assessment will be carried out.

At screening, subjects will be requested to attend the clinical center to have assessments performed as described in the Time and Events Schedule.

All results from the screening procedures required to evaluate eligibility must be available prior to drug infusion on Day 1. Any abnormal assessment at the screening visit will be assessed according to its clinical relevance, and if found relevant, the subject will not be included in the study.

On Day 1, eligibility of the subjects will be confirmed and assessments will be performed as described in the Time and Events Schedule.

Subjects will be admitted to the clinical center on Day 1 and will remain at the clinical center until at least 2 hours after study drug infusion on Day 1 and discharged if considered safe by the investigator. Prior to discharge, all subjects will be counseled on the potential GI AEs and management of these events. Subjects will have a follow-up phone call in the evening of the dosing day to ensure safety and well-being.

Follow-up Clinic Visits and Telephone Calls:

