10. ADVERSE EVENT REPORTING

10.1 DEFINITIONS

Type of Event	Collection Period
AESIs ^a	28 days after drug administration
TEAEs	Entire study period ^b
SAEs ^c and Pregnancies	Entire study period ^{b, d}

^a If a subject was enrolled with a concurrent AESI, received investigational product, and then has worsening of an AESI (severity of symptoms), then this event should also be reported.

^b The entire study period is from the time a subject receives the study drug through the Day 100 Visit.

^c If the Investigator becomes aware of any related SAE after completion of the study, he or she is obligated to report this event.

^d If a subject or the female partner of a male subject, becomes pregnant during the study or within 100 days following study drug infusion, the Sponsor must be notified within 24 hours of the site's knowledge of the pregnancy; the subject or partner will be followed until the end of the pregnancy; and the infant will be followed for 1 year after the birth, provided informed consent is obtained.

Adverse Event

An AE is any untoward medical occurrence in a patient administered a medicinal (investigational or non-investigational) product in a clinical study. An AE does not necessarily have a causal relationship with the treatment. An AE can therefore be any unfavorable and unintended sign (including an abnormal finding), symptom, or disease temporally associated with the use of a medicinal (investigational or non-investigational) product, whether or not related to that medicinal (investigational or non-investigational) product.

This includes any occurrence that is new in onset or aggravated in severity or frequency from the baseline condition, or abnormal results of diagnostic procedures, including clinical laboratory test abnormalities.

New or worsening symptoms of influenza including cough, sore throat, nasal congestion, fatigue, headache, myalgia or low-grade fever should not be reported as AEs unless they result in an SAE (i.e., lead to hospitalization).

Adverse Event of Special Interest

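### Protocol 10.8 limits pregnancy reporting to 60 days after dosing, while 10.1 requires it through the study or 100 days after infusion; the windows differ by 40 days and should be aligned

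*Protocol*

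**What the plan says.** Two sections of the protocol's adverse-event chapter set a pregnancy reporting period.

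- **Section 10.8 (Pregnancy).** The investigator must report a pregnancy in a female subject or a male subject's female partner "up to 60 days after dosing by faxing the pregnancy form to the Sponsor or designee within 24 hours" of site staff learning of it. The outcome must also be reported. Infant follow-up is not mentioned. The section opens with "Subjects should not become pregnant during the study".
- **Section 10.1 (Definitions).** The collection table places pregnancies with SAEs under the entire study period. Footnote b defines that period: "The entire study period is from the time a subject receives the study drug through the Day 100 Visit". Under footnote d, if a subject or a male subject's partner "becomes pregnant during the study or within 100 days following study drug infusion, the Sponsor must be notified within 24 hours" of the site's knowledge. The pregnancy is then followed to its end, and "the infant will be followed for 1 year after the birth, provided informed consent is obtained".

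Two statements in Section 7.1.2 bear on how these are read. Women of childbearing potential and male subjects "must practice effective contraception from screening until 60 days post-infusion", the same 60 days as in 10.8. The section closes with a pointer: "Pregnancy reporting is described in Section 10.8".

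**The concern.** Both statements are mandatory and current. They cover the same people, the same recipient and the same 24-hour clock, but they end at different times. Neither section cites the other, and no text gives either precedence.

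The likely failure runs one way. A coordinator with a pregnancy to report who follows the 7.1.2 pointer lands on 10.8, reads 60 days, and may conclude that a pregnancy beginning later need not be reported. Under 10.1 it must be. With about 150 subjects over 50–75 sites, the average is two to three subjects per site, so a site that meets a pregnancy may well be handling its first and will rely on the text.

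The stretch in dispute has no contraception requirement, and it ends around the only scheduled pregnancy test after screening, at the Day 100 or early-termination visit (Table 1). Such pregnancies can therefore come to light within the study. What could be lost is the report and the pregnancy and infant follow-up that 10.1 asks for.

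**Working it through.** The protocol gives no figure to reproduce; the check compares the two windows.

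**Inputs**

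- 10.8 window: 60 days after dosing.
- 10.1 footnote d window: during the study or within 100 days after infusion, whichever reaches further.
- Final visit: Day 100 ± 7 (Table 1), so Day 93 to Day 107.
- Dosing is Day 1, so *k* days after dosing is Day *k* + 1.
- Mean serum half-life: 12.9 days (Section 1.3, study VIS-C001).

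**Length of the gap**

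- 60 days after dosing is Day 61; 100 days after dosing is Day 101.
- Ordinary case: 100 − 60 = **40 days**, that is, pregnancies beginning 61 to 100 days after dosing (Days 62 to 101).
- Latest in-window final visit: Day 107 is 106 days after dosing, and 106 − 60 = **46 days**.
- Earliest in-window final visit: Day 93 is 92 days after dosing. The 100-day limb then governs and the gap stays at 40 days.

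**Drug remaining in that stretch.** Assuming a single-exponential decline, the fraction of the initial level left at *t* days is 2^(−*t*/12.9):

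- *t* = 61: 2^(−61/12.9) = 2^(−4.73) ≈ 3.8%
- *t* = 100: 2^(−100/12.9) = 2^(−7.75) ≈ 0.5%

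**Can both sections be met?**

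| Pregnancy begins | Reportable under 10.8 | Reportable under 10.1 |
|---|---|---|
| Up to 60 days after dosing | Yes | Yes |
| 61 to 100 days after dosing | Not required | Yes |
| After 100 days, before a late final visit | Not required | Yes |

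A pregnancy that began by day 60 and is found only at the Day 100 test falls in the first row and is not in dispute. The other two rows are the conflict.

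**Follow-up content.** The silence of 10.8 on the infant applies to every pregnancy, including those in the first 60 days. It is a separate gap, which 10.1 already fills, and does not result from the differing windows.

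**Birth-defect SAE sentence.** Section 10.8 also uses 60 days for reporting birth defects as SAEs. I leave this out. Section 10.1 collects SAEs through the Day 100 Visit and after that limits the duty: "If the Investigator becomes aware of any related SAE after completion of the study, he or she is obligated to report this event". A birth from a pregnancy that begins after day 60 would normally come well after Day 100, so widening this sentence could add a duty that 10.1 does not impose.

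**The case against.** The strongest reply is that the two sections can both be obeyed. Section 10.8 does not forbid later reports, 10.1 opens the same chapter, and Section 7.6.1 sends readers to Section 10 as a whole. That is right, and it is why the point is minor. It does not remove the conflict, because a site working to the 10.8 limit breaches 10.1, and 10.8 is the section named for pregnancy reporting.

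A second reply is that 60 days is deliberate. It matches the contraception period in 7.1.2 and in inclusion criteria 2c and 3, and residual drug is low by then. It may well be deliberate. But a contraception period and a reporting period are separate duties, and the 100 days in footnote d is equally explicit and names pregnancy. The documents do not settle which was meant. The case for the longer window is that 10.1 already requires it.

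The opening sentence of 10.8 might seem to show that the section itself looks to the end of the study. It states what is expected of subjects and sets no reporting window, so I put little weight on it.

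Finally, changing the reporting sentence alone leaves 60 days in the birth-defect sentence, so 10.8 would hold two periods. That is a fair criticism. Section 10.1 lists congenital anomaly among the SAE criteria with no 60-day limit, and 10.7 requires all SAEs to be reported whatever the suspected cause. The sponsor may reasonably want to look at that sentence too. It is a separate decision, because it concerns SAE duties after the study.

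**Conclusion.** The concern holds. Sections 10.8 and 10.1 set different mandatory windows for the same report, 40 days apart in the ordinary case and at most 46 with a final visit at the end of its window. These figures rest only on dosing being Day 1 and on the stated ± 7 days. The residual-level figures (about 3.8% falling to 0.5%) also assume single-exponential decline at the mean half-life, and they serve only to show that exposure is low in this stretch.

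No expected number of missed reports can be given: the documents state neither a pregnancy rate nor how many women of childbearing potential will enrol. With about 150 subjects it is likely to be small. Sample size, endpoints and planned analyses are untouched. This is a minor safety-reporting correction, but one that should be made.

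**What to change.** In the pregnancy-reporting sentence of Section 10.8, replace the 60-day limit with the footnote d window: during the study or within 100 days of infusion. Then either add the footnote d follow-up (to the end of the pregnancy, and of the infant for one year after birth with consent) or cross-refer to 10.1 footnote d. Leave the birth-defect SAE sentence as it is unless the sponsor decides to widen it.

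The cost is one phrase and one sentence or cross-reference, which can go into the next formal amendment under Section 12.1. No test, visit or SAE duty is added. Sites may file a few more pregnancy reports and infant follow-ups, all of which 10.1 already requires.

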10.9 REPORTING OF SAEs TO COMPETENT AUTHORITIES/ETHICS COMMITTEES

Visterra or designee is responsible for appropriate reporting of AEs to the regulatory authorities. Visterra or designee will also report to the Investigator all SAEs that are unlisted (unexpected) and associated with the use of the drug. The Investigator must report these events to the appropriate Independent Ethics Committee/Institutional Review Board (IEC/IRB) that approved the protocol, unless otherwise required and documented by the IEC/IRB.

Visterra or designee, will be responsible for unblinding and submitting SUSARs involving the study drug to the applicable regulatory authorities according to International Conference on Harmonization (ICH) guidelines. In addition, Visterra or designee, will be responsible for the submission of safety letters to the central IRB/EC and to participating Investigators of all SUSARs involving VIS410 according to applicable regulations. For clinical sites that use a local IRB/EC, it is the responsibility of the Investigator to promptly notify the local IRB/EC of all unexpected serious adverse drug reactions involving risk to human subjects.

After termination of the clinical study (determined as LSLV), any unexpected safety issue that changes the risk–benefit analysis and is likely to have an impact on the subjects who have participated in it, will be reported by the CRO as soon as possible to the competent authority(ies) concerned together with proposed actions.

11. ETHICAL ASPECTS

11.1 STUDY-SPECIFIC DESIGN CONSIDERATIONS

Potential subjects will be fully informed of the risks and requirements of the study and during the study, subjects will be provided with any new information that may affect their decision to continue participation. Subjects will be informed that their consent to participate in the study is voluntary and may be withdrawn at any time without the need to provide a reason and without penalty or loss of benefits to which they would otherwise be entitled. Only subjects who are fully able to understand the risks, benefits, and potential AEs of the study, and provide their consent voluntarily will be enrolled.

11.2 REGULATORY ETHICS COMPLIANCE

11.2.1 *Investigator Responsibilities*

The Investigator(s) should be qualified by education, training, and experience to assume responsibility for the proper conduct of the study, should meet all the qualifications specified by the applicable regulatory requirement(s), and should provide evidence of such qualifications through up-to-date curriculum vitae and/or other relevant documentation requested by the Sponsor, the IRB/IEC, and/or the regulatory authority(ies).

The Investigator is responsible for ensuring that the clinical study is performed in accordance with the protocol, current ICH guidelines on GCP, and applicable regulatory and country-specific requirements.

Good Clinical Practice is an international ethical and scientific quality standard for designing, conducting, recording, and reporting studies that involve the participation of human subjects. Compliance with this standard provides public assurance that the rights, safety, and well-being of study subjects are protected, consistent with the principles that originated in the Declaration of Helsinki; and that the clinical study data are credible.

11.2.2 *Independent Ethics Committee or Institutional Review Board*

An IRB/IEC should safeguard the rights, safety, and well-being of all study subjects. Special attention should be paid to studies that may include vulnerable subjects.

Before the start of the study, the Investigator (or Sponsor where required) will provide the IEC/IRB with current and complete copies of the following documents:

- Final protocol and, if applicable, amendments
- Sponsor-approved ICF (and any updates) and any other written materials to be provided to the subjects;
- Sponsor-approved subject recruiting materials
- Investigator Brochure (or equivalent information) and addenda
- available safety information
- information on compensation for study-related injuries or payment to subjects for participation in the study, if applicable

- Investigator's current curriculum vitae or other documentation evidencing qualifications (unless not required, as documented by IEC/IRB)
- information regarding funding, name of the Sponsor, institutional affiliations, other potential conflicts of interest, and incentives for subjects;
- any other documents that the IEC/IRB may require to fulfill its obligation

This study will be undertaken only after the IEC/IRB has given full written approval of the final protocol and amendments (if any), the ICF(s) and updates (if any), applicable recruiting materials, and any other written information to be provided to the subjects, and the Sponsor has received a copy of this approval. This approval letter must be dated and must clearly identify the IEC/IRB and the documents being approved.

During the study, the Investigator (or Sponsor where required) will send the following documents and updates to the IEC/IRB for their review and approval, where appropriate:

- protocol amendments
- revision(s) to ICF and any other written materials to be provided to subjects;
- if applicable, new or revised subject recruiting materials approved by the Sponsor;
- revisions to compensation for study-related injuries or payment to subjects for participation in the study, if applicable
- Investigator's Brochure addenda or new edition(s)
- summaries of the status of the study at intervals stipulated in guidelines of the IEC/IRB (at least annually)
- reports of AEs that are serious, unlisted, and associated with the investigational drug
- new information that may adversely affect the safety of the subjects or the conduct of the study
- deviations from or changes to the protocol to eliminate immediate hazards to the subjects;
- report of deaths of subjects under the Investigator's care
- notification if a new Investigator is responsible for the study at the site
- Development Safety Update Report, Short Term Study Specific Safety Summary and Line Listings, where applicable
- any other requirements of the IEC/IRB

For all protocol amendments (excluding the ones that are purely administrative, with no consequences for subjects, data or study conduct), the amendment and applicable ICF revisions must be submitted promptly to the IEC/IRB for review and approval before implementation of the change(s), except when necessary to eliminate immediate hazard to the study subjects. If a deviation from, or a change to the protocol was implemented to eliminate an immediate hazard to study subjects, then the implemented deviation or change, the reasons for it, and, if appropriate, the protocol amendment should be submitted to the IEC/IRB as soon as possible.

The Investigator (or Sponsor where required) will notify the IEC/IRB about the study completion within 90 days after the end of the study (defined as LSLV).

11.2.3 *Informed Consent*

Each subject must give written consent according to local requirements after the nature of the study has been fully explained. The consent form must be signed before performance of any study-related activity. The consent form that is used must be approved by both the Sponsor and by the reviewing IEC/IRB. The informed consent should be in accordance with principles that originated in the Declaration of Helsinki, current ICH and GCP guidelines, applicable regulatory requirements, and Sponsor policy.

Before enrollment in the study, the Investigator or an authorized member of the investigational staff must explain to potential subjects the aims, methods, reasonably anticipated benefits, and potential hazards of the study, and any discomfort participation in the study may entail. Subjects will be informed that their participation is voluntary and that they may refuse to participate or withdraw consent to participate at any time, without penalty or loss of benefits to which the subject was entitled. Finally, they will be told that the Investigator will maintain a subject identification register for the purposes of long-term follow up if needed and that their records may be accessed by health authorities and authorized Sponsor staff without violating the confidentiality of the subject, to the extent permitted by the applicable law(s) or regulations. By signing the ICF the subject is authorizing such access, and agrees to allow his or her study physician to re-contact the subject for the purpose of obtaining consent for additional safety evaluations, if needed.

The language used in the oral and written information about the study, including the ICF, should be non-technical and practical and should be understandable to the subject or the subject's legal representative. The subject will be given sufficient time to read the ICF and the opportunity to ask questions. After this explanation and before entry into the study, consent should be appropriately recorded by means of the subject's personally dated signature. After having obtained the consent, a copy of the ICF must be given to the subject.

If the subject is unable to read or write, an impartial witness should be present for the entire informed consent process (which includes reading and explaining all written information) and should personally date and sign the ICF after the oral consent of the subject is obtained, if permitted by local law.

11.2.4 *Privacy of Personal Data*

The collection and processing of personal data from subjects enrolled in this study will be limited to those data that are necessary to investigate the safety, quality, and utility of the investigational study drug(s) used in this study.

These data must be collected and processed with adequate precautions to ensure confidentiality and compliance with applicable data privacy protection laws and regulations. Appropriate technical and organizational measures to protect the personal data against unauthorized disclosures or access, accidental or unlawful destruction, or accidental loss or alteration must be put in place. Sponsor personnel whose responsibilities require access to personal data agree to keep the identity of study subjects confidential.

The informed consent obtained from the subject includes explicit consent for the processing of personal data and for the Investigator to allow direct access to his or her original medical

records for study-related monitoring, audit, IEC/IRB review, and regulatory inspection. This consent also addresses the transfer of the data to other entities and to other countries.

